3.2. Justification for study given risks/benefit outcome

Spinal Cord Stimulation is a commercially available neurostimulation therapy available for treatment of chronic intractable pain of the trunk and/or limbs to patients today. Traditionally, SCS leads are placed in the epidural space while the patient is awake and able to give direct feedback in order to ensure adequate paresthesia coverage. Using EMG for lead implantation will allow the patient to be placed under general anesthesia and to be potentially more comfortable than during the awake procedure. The purpose of the proposed clinical study is to collect data necessary to make a direct comparison between the awake procedure and the non-awake procedure using EMG.

The Investigator will review the subject's medical record to ensure that the subject complies with all inclusion/exclusion criteria. The target population consists of subjects indicated for a neurostimulation system. The present study will permit the physician to adhere to their standard of care for continued medication usage or any current treatment methods prior to enrollment.

The risks and benefits are the same for these two lead placement techniques since the implant procedure is the same. No additional adverse events from non-awake placement are anticipated. Considering the severity of chronic pain and its debilitating effect on patients' lives, spinal cord stimulation provides an alternative means of pain reduction with minimal risk for subjects who have exhausted other options.

4. Study Devices

All study devices are in commercial distribution in the United States and Europe as an aid in the management of chronic intractable pain of the trunk and/or limbs. St. Jude Medical (SJM) received FDA approval for the Eon Mini IPG system under the PMA P010032/S32 and Eon IPG system under the PMA P010032/S014. The Lamitrode leads received clearance under K990469 (standard), K053250 (90 and 110cm), K033429 (C-Series), K022222 (S-Series), K063080 (Tripole 8C, 16C, and Exclaim), K090907 (Penta) and K991784 (extensions).

Any SJM market-cleared IPG may be used. Any SJM market-cleared paddle lead may be used. Percutaneous leads may not be used.

The Eon Rechargeable Systems consists of the following components: Model 3716 and 3788, Rechargeable Implanted pulse generator (IPG), Model 3851 Patient Programmer, Programming Wand, Patient Magnet, and Charging System. The Eon Neurostimulation Systems are intended to be used with SJM's leads and extensions and their accessories currently on the market.

5. Patient Selection

5.1. Inclusion Criteria

Patients enrolled in this study must meet the following inclusion criteria:

1. Patient is able to provide informed consent to participate in the study
2. Patient is 18 years of age or older
3. Patient has had a successful trial system and is presenting for permanent implantation of a paddle electrode in thoracic region.
4. Patient is willing to cooperate with the study requirements including compliance with the treatment regimen and completion of all office visits

5.2. Exclusion Criteria

A patient will be excluded from participation in this study if they meet any one of the following criteria:

1. Patient currently participating in a clinical investigation that includes an active treatment arm.
2. Patient has an infusion pump or any implantable neurostimulation device
3. Patient has an existing medical condition that is likely to require repetitive MRI evaluation in the future (i.e. epilepsy, stroke, multiple sclerosis, acoustic neuroma, tumor)
4. Patient has an existing medical condition that is likely to require the use of diathermy in the future
5. Patient is immunocompromised
6. Patient has documented history of allergic response to titanium or silicone
7. Patient has a documented history of substance abuse (narcotics, alcohol, etc.) or substance dependency in the 6 months prior to baseline data collection
8. Female candidates of child bearing potential that are pregnant (confirmed by positive pregnancy test)

6. Patient Assignment to Procedure

Each patient who is willing to participate in the study, signs the informed consent, and complies with the inclusion/exclusion criteria will be enrolled in the study. Patients are considered enrolled in the study from the moment the patient has provided written informed consent. Each patient is enrolled chronologically on a patient enrollment log and given a patient number for the duration of the study.

Patients will be enrolled in a 1:1 fashion to the method of surgical implantation, either awake or non-awake. Patients will be treated by the enrolling physician. Patients recruited and enrolled at St. Luke's Neurological Associates or Thomas Jefferson University will undergo implantation under general anesthesia with EMG neuromonitoring for testing of the distribution of induced paresthesia ("non-awake"). Patients recruited and enrolled at Geisinger or Milton S. Hershey Medical Centers will undergo implantation of the device in an awake operation with local anesthetic and patient interaction for testing of the distribution of the induced paresthesia ("awake"). Each treatment arm will enroll a maximum of 30 patients. No blinding is necessary for the purposes of assigned study arm.

7. Methods and Procedures

7.1. Informed Consent

Written informed consent must be obtained from all patients before recruitment into the study. All potential patients must be properly informed as to the purpose of the study and the potential risks and benefits known or that can be reasonably predicted or expected. The Investigator will retain the original copy of the Informed Consent Form signed by the patient and a duplicate will be provided to the patient. Only the consent form approved by the applicable Institutional Review Board (IRB) must be used.

7.2. Screening

The patient is evaluated for eligibility according to the inclusion/exclusion criteria. This evaluation will include a report of medical history, current medication regimen, and completion of questionnaires. At the end of the study visit after the investigator has determined that the patient is eligible for participation, study staff (e.g. study coordinator) collect the following information:

- Enrollment form
- Inclusion/exclusion form

7.3. Randomization

Patients will not be randomized. .

7.4. Baseline Evaluation

Baseline measurements for the patient's back and leg pain symptoms and general well-being will be taken. This evaluation will include a report of medical history, current medication regimen, and completion of questionnaires. Baseline evaluations include the following activities:

- Collection of self-reported patient questionnaires:
 - Baseline self-evaluation form
 - Pain Location form
 - Pain Evaluation form
 - SF-MPQ-2 (Pain Quality)
 - EQ-5D (Quality of Life)
 - Medication Usage form

7.5. Medication Collection

Since certain non-pain medications have the ability to affect pain (e.g. certain antidepressants), we are collecting other medication usage outside of pain management medication. However, medications taken for common cold and allergies will not be recorded.

7.6. SCS Permanent System Implantation Guidelines

This section of the protocol provides a guideline for surgical implantation of the permanent system; however, implantation of the devices is performed at the discretion of the Investigator. The goal of the surgery is to enable coverage of the patient's entire

painful area with stimulation. Patients will be prepped for surgical paddle lead placement via laminectomy or laminotomy according to usual practice at each implanting center, including anesthesia and customary intraoperative monitoring. Initial lead placement is targeted anatomically based on patient-specific painful areas and trial lead experience.

7.6.1. Lead Placement for Awake Arm

Upon approximate lead positioning, the patient is brought to a conscious sedated state while maintaining local anesthetic. Stimulation of the spinal cord through the paddle lead is accomplished with an external pulse generator, while communicating with the patient regarding paresthesia coverage of painful regions. Upon satisfactory coverage, the IPG is implanted per 7.6.3 below.

7.6.2. Lead Placement for Non-awake Arm

The patient is maintained under general anesthesia for the full duration of the implant. Upon approximate lead positioning, bilateral EMG of myotomes overlapping dermatomal regions of pain are monitored. Stimulation is delivered through the lead by an external pulse generator in order to elicit compound muscle action potentials (CMAPs) in the target regions. Lead placement is targeted to have symmetric CMAPs (i.e. physiologic midline) and adequate coverage of the painful regions as described by Falowski et al. (Falowski et al., 2011). Upon satisfactory coverage, the IPG is implanted per 7.6.3 below.

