3.1. Design

This is a post-market, prospective, multicenter, parallel designed, non-randomized, non-blinded, 6-month study. A minimum of 50 patients will be implanted from up to 4 active sites, coordinated by a single lead investigator.

Patients who have had a successful SCS trial and are indicated for permanent implantation will be approached to participate in this study prior to permanent implantation. Patients will be recruited and enrolled by physicians at any one of the involved sites. Each Investigator will only use one method (awake or non-awake) according to his/her typical practice. Patients will receive treatment from their enrolling physician.

[figure not shown]

Table 1: Study Schedule

Timing of visit	Activities at visit	Case Report Forms
Screening and Informed Consent (may be immediately after Trial System Explant)	Patient evaluated for eligibility Patient signs informed consent Schedule patient for baseline evaluation at treatment site	Enrollment Form Inclusion/Exclusion Criteria Form
Baseline Evaluation 7-28 days after screening	Patient completes questionnaires Complete history and physical exam Record current medication use Collect patient reported data	Baseline Self Evaluation Form Pain Location Form Pain Evaluation Form SF-MPQ-2 (Pain Quality) EQ-5D (Quality of life) Medication Form
Permanent System Implantation	Permanent system implantation Record any complications Record any changes in medication Discourage activation at discharge Save digital recording or EMG recording if system permits.	Surgery Form Adverse Event Form Programming Form (if programmed at discharge) Medication Form
Initial Programming Visit	Record any complications Record any changes in medication Provide patient with the patient programmer and charging system Record patient's global impression of satisfaction with the implant procedure.	Programming Form Paresthesia Coverage Form Patient Global Impression Form Medication Form
6 weeks 42 ± 7 days after activation	Record any complications Record any changes in medication Patient completes questionnaires Modify programming parameters (if necessary) Collect patient reported data	Follow-up Visit Form Pain Evaluation Form Pain Location Form Programming Form SF-MPQ-2 (Pain Quality) EQ-5D (Quality of life) Paresthesia Coverage Form Medication Form

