7.11.3. Coverage

As described below, paresthesia coverage of painful regions will be measured by comparing pain maps to paresthesia maps. Adequate coverage of painful regions with paresthesia and avoidance of paresthesia outside of painful regions will be assessed.

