10.4. Secondary Analysis

10.4.1. Paresthesia coverage

Hypothesis:

The non-awake is comparable to the awake method in the proportion of the painful regions covered by paresthesia

Metrics:

Paresthesia overlap percentage

Extraneous paresthesia percentage

The regions marked on the Pain Location Form and Paresthesia Coverage form will be categorized as overlapping, uncovered pain, excess paresthesia, or none (see Table 3; Alo, Yland, Redko, Feler, & Naumann, 1999).

$$paresthesia\ overlap\ percentage = \frac{N_O}{N_U+N_O} \cdot 100$$

$$extraneous\ paresthesia\ percentage = \frac{N_E}{N_O+N_E} \cdot 100$$

Statistical Tests:

Test for normality (such as Jarque-Bera)

Unpaired, two-sided Student’s t-tests (normally distributed continuous data) or Mann-Whitney rank sums test (skewed continuous data)

Significance at $\alpha < 0.05$, with no adjustment for the multiple comparisons

		Paresthesia Coverage Form	
		Marked	Unmarked
Pain Location Form	Marked	Overlap N_O	Uncovered N_U
	Blank	Excess N_E	None N_N

Table 3: Pain-Paresthesia Comparison Categories

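### Extraneous paresthesia percentage depends on whether pain is one-sided, but section 10.4.1 compares it between site-allocated arms without any laterality factor

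*Combined protocol and SAP*

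**What the plan says.** Section 7.11.3 makes wrong-site stimulation an outcome alongside coverage: "avoidance of paresthesia outside of painful regions will be assessed". Section 10.4.1 turns this into the metric "Extraneous paresthesia percentage", defined as N_E/(N_O+N_E) × 100. N_O counts map regions marked for both pain and paresthesia, and N_E counts regions marked for paresthesia only. The arms are compared with an unpaired t-test or a Mann-Whitney test at 5%. No covariate, stratum or subgroup is named, and section 10.5 adds only summary statistics and possible post-hoc work.

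The arms are not randomised. Section 3.1 states: "Each Investigator will only use one method (awake or non-awake) according to his/her typical practice". Section 6 assigns two sites to each method. The eligibility criteria in sections 5.1 and 5.2 do not mention the side of pain.

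On placement, section 7.6.2 (non-awake) says "bilateral EMG of myotomes overlapping dermatomal regions of pain are monitored" and "Lead placement is targeted to have symmetric CMAPs (i.e. physiologic midline) and adequate coverage of the painful regions". Section 7.6.1 (awake) relies on "communicating with the patient regarding paresthesia coverage of painful regions" and names no symmetry criterion. Section 7.6 applies to both arms: "Initial lead placement is targeted anatomically based on patient-specific painful areas and trial lead experience".

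Appendix A schedules the Pain Location Form at baseline, 6 weeks and 24 weeks.

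**The concern.** The denominator of the extraneous metric is everything the patient feels as paresthesia. Paresthesia on the side opposite the pain counts as excess only if that side is pain-free. The same field therefore scores differently according to where the patient hurts, before any effect of the implant method.

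Three consequences follow for a comparison that ignores laterality:

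- **Case mix.** Each site supplies one arm, so a different share of one-sided pain between sites appears as a difference between methods.
- **Noise.** With equal shares, the spread between one-sided and two-sided patients still widens the interval, although a baseline variable could remove part of it.
- **Dilution.** If the methods differ only in one-sided pain, the pooled contrast shrinks in proportion to the share of such patients.

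At stake is the reading of one of the two metrics under the secondary objective.

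**Working it through.** The plan gives no assumed value, SD or power for extraneous paresthesia, so there is no figure of its own to reproduce.

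**1. Arithmetic of the metric (Table 3 and the formula in 10.4.1).**
- One-sided pain in k regions, mirrored field: N_O = k, N_E = k, so 100 × k/(k+k) = 50% for any k.
- Symmetric two-sided pain in 2k regions, same field: N_O = 2k, N_E = 0, so 0%.
- Overlap percentage, N_O/(N_U+N_O), is 100% in both cases.

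**2. Inputs for the illustration.** From the documents: a minimum of 50 patients, enrolled 1:1, hence 25 per arm. Assumed: left and right are separate map regions; mean 50% for one-sided pain with a mirrored field and 5% otherwise; residual SD 15 points; values not truncated to 0-100; no method effect; either half or all of the one-sided patients have a mirrored field. The shares of one-sided pain are also assumed.

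**3. Spurious gap.** Gap = (difference in shares) × (fraction mirrored) × (50 − 5).
- Shares 50% vs 30%: 0.20 × 0.5 × 45 = 4.5 points; 0.20 × 1 × 45 = 9.0 points.
- Shares 50% vs 20%: 0.30 × 0.5 × 45 = 6.75 points; 0.30 × 1 × 45 = 13.5 points.

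Simulated rejection rates at nominal 5%:

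| One-sided shares | Unadjusted Mann-Whitney | With laterality term |
|---|---|---|
| 50% vs 30% | 9-22% | about 4-6% |
| 50% vs 20% | 13-42% | about 4-6% |

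Imbalance need not be systematic. If the true share is 30% in both arms, an observed gap of 20 points or more arises by chance in about 16% of trials with 25 per arm.

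**4. Noise with equal shares (40% one-sided in both arms).** SE of the arm difference = √(2 × variance/25).
- Half mirrored, unadjusted: variance 225 + 45² × 0.2 × 0.8 = 549, SE 6.6. Adjusted: 0.4 × (225 + 45² × 0.25) + 0.6 × 225 = 427.5, SE 5.8.
- All mirrored, unadjusted: 225 + 45² × 0.4 × 0.6 = 711, SE 7.5. Adjusted: 225, SE 4.2.

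**5. Dilution.** A 25-point method difference confined to one-sided pain pools to 25 × share: 5 points at 20%, 7.5 at 30%, 10 at 40%. A separate simulation used means of 50 and 25 in one-sided pain by arm and 15 in two-sided pain, SD 20, values held within 0-100. At a 30% share the pooled t-test had 22% power, a model with a laterality main effect 26%, and a test within one-sided patients 60%. A main-effect term therefore does not reveal such a difference; the estimates by laterality are needed for that.

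**The case against.** The strongest reply is that the placement contrast is weaker than it looks. A reader might infer that non-awake leads go to the midline whatever the side of the pain while awake leads follow the pain. The documents do not support that. Section 7.6.2 asks for symmetry jointly with adequate coverage, in myotomes matched to the pain. Section 7.6 bases initial placement on the painful areas in both arms and leaves implantation to the investigator. Both arm-specific sections end on satisfactory coverage. Paresthesia is mapped after individual programming (section 7.8) and can be reprogrammed later, so lead position does not fix the field, and 50% is the fully mirrored extreme. This stands: the contrast is one of degree, and a method effect confined to one-sided pain is only a possibility.

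A reader might also infer that the comparable-coverage hypothesis itself is undermined. That hypothesis concerns the proportion of painful regions covered, and overlap percentage is unchanged in the example above. No effect on it has been shown.

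Next, section 7.12 speaks only of numbered regions on the Pain Location Form. If they do not separate left from right, the case-mix and noise arguments fall away; the metric would then be blind to wrong-side paresthesia.

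Finally, confounding by site is a general weakness of this design, and the pooled contrast is a legitimate average comparison of the methods as practised. Both points are true. Neither is a reason to omit a factor that enters the metric by construction and comes from a form already collected. The case-mix calculation assumes no method effect, so it does not depend on the placement contrast.

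**Conclusion.** The point holds for extraneous paresthesia percentage. The metric depends on pain laterality by arithmetic, allocation by site gives no protection against unequal laterality, and 10.4.1 plans no adjustment. On the assumptions above, a 20-point imbalance in one-sided pain gives a spurious gap of about 5 to 9 points and 9-22% false positives, returned to about 4-6% by adjustment. With equal shares there is no systematic bias, only chance imbalance and avoidable noise. The sizes rest on assumed means, SD and shares, and on separate left and right map regions; none of these is in the documents. This is a worthwhile improvement to one secondary metric. It does not show that the arms are placed to opposing targets or that the overlap comparison is invalid.

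**What to change.** First confirm that the numbered map regions separate left from right. Then, in section 10.4.1:

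- Derive pain laterality from the baseline Pain Location Form: one-sided if all marked regions lie on one side, otherwise two-sided. Report the distribution by arm.
- Pre-specify that extraneous paresthesia percentage is compared with this factor included, by a linear model or a van Elteren stratified rank test. The same adjustment for overlap percentage is optional.
- Report the arm difference with a 95% CI within each laterality group, labelled descriptive. Do not tie a claim of comparability to those intervals, since 10.4.1 sets no margin against which to judge them.

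The cost is one derived variable and a few lines of analysis text, with no new data and no change to surgical practice. The drawback is precision: with 20-40% one-sided (5 to 10 per arm) and SD 15, the 95% half-width in that group is about 22 to 14 points.

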7.6.3. Pulse Generator Placement and Data Collection for Both Arms

The IPG is implanted by making a pocket incision at the desired location, and creating a subcutaneous pocket by blunt dissection. The pocket should be created so that the IPG is parallel to the skin surface. Subcutaneous tunnels are made from the lead incision site(s) to the IPG implantation site, using a tunneling tool. The leads/extension is tunneled to the IPG site. The lead/extension is connected to the IPG, the IPG is placed in the subcutaneous pocket, and all incisions are closed.

Additional guidance on system placement is located in the device manuals distributed with each device.

System implantation visit include recording the following information:

- Device information
- Collection of complications or changes in medication
- Total operating room time
- Skin-to-skin surgical time
- Intraoperative programming time
- Total fluoroscopy used (time and dose)
- Final lead position

7.7. Postoperative Management and Instruction

The physician will provide normal standard of care after implantation of the system, including standard post-operative monitoring. Instructions for wound care and monitoring will be provided to the patient by the implanting physician. Patients will be informed to report any adverse events or changes in medication to study personnel. Patients will be informed not to manipulate the leads after implantation because tissue erosion may occur. The patient will be sent home for a 2-3 week recovery period to let any swelling and/or post-operative pain subside prior to activation of SCS system, unless otherwise

determined by the installing investigator. During this time, the device may not be activated and the patient may not be provided with the Patient Programmer. Prophylactic antibiotic therapy may be instituted at the discretion of the Investigator.

If the leads migrate during the study, the implanting physician will examine the area of implantation. The leads can be repositioned or re-implanted if mutually agreed upon by the physician and the patient. The patient and the implanting physician will make the mutual decision about any possible revision of the device based upon what is medically safe, what is desired by the patient, and what is in the patient's best medical interests.

If an infection occurs, standard medical practice suggests that the leads be removed and the patients undergo a standard course of oral antibiotics. Any infection or wound will be given time to heal before any re-implantation is attempted.

If the device is completely explanted from the study patient for any reason and re-implantation is not an option, then the patient will exit the study.

